# **5.3** Subject Disposition

The number and percentage of subjects who were enrolled, dosed, completed, or early discontinued will be displayed. Reasons for early discontinuation will include:

- Adverse event
- Lost to follow-up
- Investigator decision
- Administrative reason
- Failure to follow required study procedures
- Withdrawal by subject and other.

#### **5.4** Protocol Deviations

Protocol deviations will be presented in listings. Protocol deviations may include, but are not limited to:

- Non-compliance with any scheduled study visit
- Non-compliance with study treatment
- Disallowed concomitant medications
- Non-compliance with study inclusion or exclusion criteria
- Non-compliance with study assessment procedures

# **5.5** Demographic Characteristics

Descriptive statistics for Age, Baseline Height, Weight, and BMI will be presented using n, mean, STD, Min and Max. Frequencies and percentages will be presented for Race, Ethnicity and Sex.

## **5.6** Study Drug Exposure

Duration of exposure in days will be calculated from the first and last dates of the study drug administration. The duration of exposure will be calculated as date of last dose minus date of first dose + 1. Duration of exposure (days) will be summarized by categories and descriptive statistics. The categories for duration of exposure are Weeks 1-2 (Titration period), Weeks 3-5 (Maintenance Period).

## **5.7** Handling of Missing Data

There will be no substitutions made for missing data points. The number of missing values will be presented in the analysis tabulations, as applicable, but without a percentage.

### 6 EFFICACY ANALYSES

The efficacy analysis will be based on the safety population for subjects who have sufficient baseline and post baseline IA diary to calculate percent change as defined below.

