8.3 Analysis Populations

The population of "all enrolled subjects" consists of all those screened subjects who meet the requirements for study participation and are entered in the Baseline period of the study. The population of "all randomized subjects" consists of all those enrolled subjects who complete the Baseline Period, meet the inclusion/exclusion criteria and are randomized.

Safety Population: will include all subjects who received at least 1 dose of study drug and had at least one post-baseline safety assessment.

Full Analysis Set (FAS): will include all screened subjects who received at least 1 dose of study drug and have completed baseline and at least 1 valid post-randomization assessment of frequency of IA behaviors based on IA diary entry.

Per-Protocol (PP) Population: will include all subjects who completed Treatment Phase and did not have major protocol deviations (as defined in the SAP).

PK population: will include all subjects in the safety population who have received at least 1 dose of study drug and had one PK sample drawn which had quantifiable concentration for molindone.

The safety, psychometric, FAS, PP, and PK populations are based on randomized treatment received.

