### **5 STATISTICAL METHODS and ANALYSES**

#### **5.1** General Considerations

Because SPN-810 did not show efficacy for the Treatment of Impulsive Aggression in the two previous Double-Blind Studies (810P301 and 810P302), the conduct of this study (810P503) was halted. Therefore, the analysis will be limited to the primary, key secondary endpoints and safety data, which will include adverse events (AEs), Extrapyramidal Symptoms (EPS), Simpson-Angus Scale, Barnes Akathisia Scale, and Abnormal Involuntary Movement Scale, clinical laboratory evaluations, vital signs, suicidal symptoms (C-SSRS) and ECG results.

All descriptive statistical analyses will be performed using SAS (Version 9.4), unless otherwise noted and will be presented by treatment groups (Placebo, SPN-810).

Continuous variable summaries will include the number of subjects (n) with non-missing values, mean, standard deviation (SD), median, interquartile range (Q1 and Q3), minimum, and maximum.

Categorical variable summaries will include the frequency and percentage of subjects who are in the category or each possible value. In general, the denominator for the percentage calculation will be based upon the total number of subjects in the study population for the treatment groups, unless otherwise specified. The denominator for by visit displays will be the number of subjects in the relevant study population with non-missing data at each study visit.

In general, the baseline value for a variable is defined as the last observation prior to the first dose of double-blind study medication, ideally Visit 3, but including the screening value, if necessary.

All data will be presented in Listings.

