# **5.2** Analysis Population

The population of "all enrolled subjects" consists of all those screened subjects who meet the requirements for study participation and are entered in the Baseline period of the study. The population of "all randomized subjects" consists of all those enrolled subjects who complete the Baseline Period, meet the inclusion/exclusion criteria and are randomized via the The safety population will include all subjects who received at least 1 dose of study drug and has at least one post-baseline safety assessment.

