## **6.1** Primary efficacy endpoint

The primary efficacy endpoint, percent change (PCHT) in the frequency (unweighted score) of IA behaviors per 7 days, will be calculated as  $PCH_T = 100*(T - B)/B$ , where T and B are IA behavior frequencies per 7 days during the Treatment Phase (titration + maintenance periods) and Baseline period, respectively. The IA behavior frequency per 7 days is defined as (SUM/DAY) x 7, where SUM is the total of the 15 IA behaviors reported in IA diary, and DAY

is the number of days with non-missing IA score in the IA diary during the specified study period.

PCHT will be summarized by treatment groups as described for continuous variables in Section 5.1. Individual subject listings supporting the summary will be presented.

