# **6.2** Key Secondary Endpoints

The absolute and change from baseline for CGI-S and R-MOAS will be summarized by treatment groups and visit using descriptive statistics for continuous variables as described Section 5.1.

The CGI-S is evaluated on a 7-point scale, where 1 = Normal, not at all ill, asymptomatic, 2 = Borderline Ill, 3 = Mildly Ill, 4 = Moderately Ill, 5 = Markedly Ill, 6 = Severely Ill, and 7 = Extremely Ill.

The percentage of subjects with remission of R-MOAS  $\leq$  10 will be summarized by treatment groups and visit using descriptive statistics for categorical variables as described Section 5.1.

Individual subject listings supporting the summaries will be presented.

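### Read literally, SAP Section 6 makes a usable treatment-phase IA diary a condition for every efficacy summary, including CGI-S and R-MOAS, although only the percent change in IA behaviors needs it.

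*SAP*

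**What the plan says.** The SAP has one population statement for efficacy, the lead-in to Section 6. Within the safety population, it limits the efficacy analysis to "subjects who have sufficient baseline and post baseline IA diary to calculate percent change as defined below". It points forward to the definition of percent change, which appears only in 6.1. There, the DAY term of the formula "is the number of days with non-missing IA score in the IA diary during the specified study period". No minimum number of days is given.

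Section 6.2 follows with no population of its own: "The absolute and change from baseline for CGI-S and R-MOAS will be summarized by treatment groups and visit". The R-MOAS remission percentage likewise "will be summarized by treatment groups and visit using descriptive statistics for categorical variables as described Section 5.1". Section 6.3 (CGI-I, caregiver CGI-S, CHQ-PF28, SNAP-IV, SIPA) also names none.

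SAP 5.2 defines enrolled, randomized and safety populations but no Full Analysis Set. Its safety definition has no diary condition: "The safety population will include all subjects who received at least 1 dose of study drug and has at least one post-baseline safety assessment".

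Protocol 8.3 does define a Full Analysis Set, and membership requires, among other things, "at least 1 valid post-randomization assessment of frequency of IA behaviors based on IA diary entry".

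**The concern.** A condition that makes sense for one endpoint has been placed where it governs all of them. CGI-S, R-MOAS, R-MOAS remission and the 6.3 scales are not computed from diary data, so the absence of a diary is no reason to leave out their observed values.

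Two things are at stake. Ratings already collected go unused in the tables of a study that was halted. Inclusion also depends on something that happens after randomization, namely whether a caregiver completes the diary, which has no bearing on whether the other scales can be summarized. The Investigator CGI-S is first in the testing order for the key secondary endpoints in Protocol 9.2, and it is the one key secondary not rated by a parent. Tying it to caregiver diary use reduces its value as a separate check.

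There is also a reproducibility problem: with *sufficient* undefined, two programmers could arrive at different n for every table in Section 6.

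**Working it through.** The plan gives no figure on this point, so the check compares the texts and works through the formula.

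**1. Does other SAP text bring the subjects back?** No.
- SAP 5.1 says of by-visit displays: "The denominator for by visit displays will be the number of subjects in the relevant study population with non-missing data at each study visit". That count works inside the relevant population and does not widen it.
- SAP 5.7 makes no substitution for missing data, so an absent diary cannot be filled in.
- SAP 5.1 does put all data in listings, so the ratings remain visible there.

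**2. Which endpoints need the diary?** Rater and source, from Protocol 6.1 and 6.2:
- PCH_T: caregiver IA diary.
- Investigator CGI-S: investigator.
- R-MOAS, and so remission: parent, recalling the past week.
- CGI-I: investigator and caregiver.
- Caregiver CGI-S, SNAP-IV, CHQ-PF28, SIPA: caregiver or parent.

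Only the first uses diary data.

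**3. When can PCH_T not be calculated?** The formula is PCH_T = 100 × (T − B)/B, with T and B each equal to (SUM/DAY) × 7 over their own period.
- B: randomization requires at least 70% diary compliance (0.70 × 15 = 10.5, so 11 of 15 days) and a baseline score of at least 6 per 7 days. For eligible subjects B exists and is not zero, so the condition bites on the treatment phase.
- T with DAY = 0: undefined, and the subject is out.
- T with DAY = 1: T = 7 × SUM. For a subject at the entry threshold, B = 6, with one diary day and no behaviors, T = 0 and PCH_T = 100 × (0 − 6)/6 = −100%. With one behavior on that day, T = 7 and PCH_T = 100 × (7 − 6)/6 = 16.7%.

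One day therefore satisfies the condition arithmetically. The two one-day results also show why a stated minimum is wanted.

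**4. Can a subject have ratings but no treatment-phase diary day?** Yes, by two routes.
- *Attends Visits 4 to 7 without diary entries.* The 70% rule applies at randomization only, and no numeric floor applies afterwards. The first scheduled post-baseline CGI-S is at Visit 4 (Day 15), so losing a CGI-S value this way needs about two weeks with no entry at all.
- *Stops before Visit 4.* Protocol 5.3.8 and 5.7 bring such subjects back to complete the Visit 8 procedures, which include R-MOAS and safety assessments. The subject is then in the safety population with a post-baseline R-MOAS, but is excluded if no diary day was recorded. The Visit 8 list in 5.3.8 contains no CGI-S, so this route affects R-MOAS and remission.

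**5. How many?** The documents give neither the number actually randomized before the halt nor any rate of empty treatment-phase diaries, so no count follows.

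**The case against.** The strongest reply is that very few subjects can be affected. Diary recording in the Treatment Phase starts on Day 1, one day suffices by the formula, every randomized caregiver has already completed at least 11 of 15 baseline days, and the Visit 4 to 7 procedures in Protocol 5.3 have sites review diary compliance and retrain. A wholly empty treatment diary in a subject who still returns for ratings should be uncommon. This stands.

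The restriction also did not originate in the SAP, since the protocol's Full Analysis Set has a similar condition. One common efficacy set with a single n is a recognised choice. This stands too, although Protocol 9.1 ties that set to the primary hypothesis while 9.2 names no population for the secondary scales.

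Finally, SAP Section 6 specifies no test, model or confidence interval, and the excluded ratings are still listed. SAP 5.1 also limits the analysis to primary, key secondary and safety data, so the 6.3 scales matter only if their tables are produced. This limits the consequence to descriptive tables.

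None of it supplies a reason to require a diary for scales that do not use one, and no text exempts 6.2 or 6.3.

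**Conclusion.** The point holds on the plain wording and is minor. Section 6 restricts every efficacy summary to subjects with a usable baseline and post-baseline diary, and only PCH_T needs that. The effect is confined to subjects with ratings but no usable treatment-phase diary. Their number cannot be derived and is probably small.

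Stronger readings that a reader might infer are not supported:
- *A caregiver who stops the diary part-way removes the subject.* Not by the formula; one treatment-phase day keeps the subject in. Exclusion of such subjects requires a stricter meaning of *sufficient* than the SAP states.
- *Diary use is unmonitored after randomization.* There is no floor, but compliance is reviewed at Visits 4 to 7.
- *All the key secondaries are independent of the caregiver.* R-MOAS and remission are parent-rated, so rater independence applies mainly to the Investigator CGI-S.
- *A sizeable share of the planned 186 is lost.* Any percentage applied to 186 would be a guess, because the study was halted and the documents give no number randomized.
- *The tables are biased by a treatment effect on diary completion.* Selection on a post-randomization behavior is a possibility; no text links treatment to diary completion.

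The conclusion assumes that the Section 6 lead-in means what it says for 6.2 and 6.3. If it was meant for PCH_T only, the text needs the same correction.

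**What to change.** Move the diary condition from the Section 6 lead-in into SAP 6.1, so that it applies to PCH_T only, and state there the minimum number of non-missing diary days required in the baseline and treatment periods, replacing the word *sufficient*.

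For 6.2 and 6.3, specify that each scale is summarized in all safety-population subjects with a baseline and at least one post-baseline value of that scale. For CGI-I, which has no baseline rating, require at least one post-baseline rating.

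The cost is a few lines of SAP text and one population flag per endpoint. No new data are needed. The downside is that n will differ slightly between the primary and secondary tables, which a footnote can explain.

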## **6.1** Primary efficacy endpoint

The primary efficacy endpoint, percent change (PCHT) in the frequency (unweighted score) of IA behaviors per 7 days, will be calculated as  $PCH_T = 100*(T - B)/B$ , where T and B are IA behavior frequencies per 7 days during the Treatment Phase (titration + maintenance periods) and Baseline period, respectively. The IA behavior frequency per 7 days is defined as (SUM/DAY) x 7, where SUM is the total of the 15 IA behaviors reported in IA diary, and DAY

is the number of days with non-missing IA score in the IA diary during the specified study period.

PCHT will be summarized by treatment groups as described for continuous variables in Section 5.1. Individual subject listings supporting the summary will be presented.

# **6.2** Key Secondary Endpoints

The absolute and change from baseline for CGI-S and R-MOAS will be summarized by treatment groups and visit using descriptive statistics for continuous variables as described Section 5.1.

The CGI-S is evaluated on a 7-point scale, where 1 = Normal, not at all ill, asymptomatic, 2 = Borderline Ill, 3 = Mildly Ill, 4 = Moderately Ill, 5 = Markedly Ill, 6 = Severely Ill, and 7 = Extremely Ill.

The percentage of subjects with remission of R-MOAS  $\leq$  10 will be summarized by treatment groups and visit using descriptive statistics for categorical variables as described Section 5.1.

Individual subject listings supporting the summaries will be presented.

# **6.3** Additional Secondary Endpoints

The absolute value of investigator-rated Clinical Global Improvement (CGI-I) scale, Caregiver-rated CGI-I scale and Caregiver-rated CGI-S scale will be summarized the same way as for CGI-S described in the above Section.

The CGI-I is evaluated on a 7-point scale, where 1 = Very much improved, 2 = Much improved, 3 = Minimally improved, 4 = No change,5 = Minimally worse,6 = Much worse, and 7 = Very much worse.

The absolute Caregiver-rated CGI-S scale score and change from baseline will be summarized the same as for CGI-S as described above.

With respect to CHQ-PF28, z-score will be derived and be summarized by treatment group at visit 1 and 7. The recorded score needs to be transformed in 0-100 range before calculating subscales and summary scores.

CHQ-PF28 Questionnaire Item	Recorded on CRF	Final Raw	Transformed Score
1.1;	1	5	((Final -1)/4) * 100
5.2;	2	4.4	
9.4	3	3	
	4	2.2	
	5	1	
2.1a-2.1c;	1	1	((Final -1)/3) * 100
3.1;	2	2	

3.2;	3	3	
9.2	4	4	
4.1	1	6	((Final -1)/5) * 100
	2	5	
	3	4	
	4	3	
	5	2	
	6	1	
5.1a-5.1c;	1	1	((Final -1)/4) * 100
6.1a-6.1c;	2	2	
8.1a-8.1c; 9.3a-9.3b	3	3	
	4	4	
	5	5	
	1	5	((Final -1)/4) * 100
7.1a-7.1c;	2	4	
8.2; 9.1a-9.1b	3	3	
	4	2	
	5	1	

The physical functioning (PHS) and psychosocial health (PSS) summary scores are calculated in three steps.

• Step1: z-score standardizations.

Subscale	Sum of items	Formulas for z-score standardizations
Physical Functioning (PF)	2.1a-2.1c	PF_Z=(PF - 90.8525408) / 16.3826344
Role/Social Limitations - Physical (RP)	3.2	RP_Z=(RP - 91.4951246) / 18.9079749

General Health Perceptions (GH)	8.1a-8.1c,1.1	GH_Z=(GH - 66.6958379) / 19.3564297
Bodily Pain/Discomfort (BP)	4.1	BP_Z=(BP - 78.6833515) / 20.7355708
Role/Social Limitations - Emotional/Behavior (REB)	3.1	REB_Z=(REB - 90.4013015) / 19.5067502
Parental Impact - Time (PT)	9.2a-9.2b	PT_Z=(PT - 83.8816188) / 20.2901603
Parental Impact - Emotional (PE)	9.1a-9.1b	PE_Z=(PE - 73.9788476) / 21.406013
Self-Esteem (SE)	7.1a-7.1c	SE_Z=(SE - 79.2555314) / 17.8308361
Mental Health (MH)	6.1a-6.1c	MH_Z=(MH - 77.2595806) / 13.6861999
Behavior (BE)	5.1a-5.1c,5.2	BE_Z=(BE - 72.3086051) / 17.1447913
Family Activities (FA)	9.3a-9.3b	NA
Global Health (GGH)	1.1	NA
Global Behavior (GBE)	5.2	NA
Family Cohesion (FC)	9.4	NA
Change in Health (CH)	8.2	NA

• Step 2. PHS and PSS raw scores

+ (BE Z \* .27911)

• Step 3. Transformation of PHS\_raw and PSS-raw

Transformed physical (PHS) = 50 + (PHS raw \* 10)

Transformed psychosocial (PSS) = 50 + (PSS raw \* 10)

More details can be found in the Child Health Questionnaire (CHQ) Scoring and Interpretation Manual (HealthActCHQ).

The ratings from the SNAP-IV scale are grouped into the following 4 subscales:

• ADHD-Inattention (items #1-9),

- ADHD-Hyperactivity/Impulsivity (items #10-18)
- ADHD-Combined subscales (items #1-18)
- Oppositional Defiant Disorder (ODD) (items #19-26)

Each subscale score is calculated by averaging the items scores within each subscale.

The absolute and change from baseline for SNAP-IV will be summarized by treatment group at visit 7.

Stress Index for Parents of Adolescents (SIPA) rating scale includes 112 items. The first 90 items use a 5-point rating scale ranging from Strongly Disagree (5) to Strongly Agree (1): 1=SD (Strongly Disagree), 2=DA (Disagree), 3=NS (Not Sure), 4=A (Agree), and 5=SA (Strongly Agree).

Note: Items 2, 3, 4, 5, 9, 10, 15, 25, 28, 34, 40, 45, 49, 54, 66, 69, 74, 81, 83, 85, 87, and 88 are rated from Strongly Disagree (5) to Strongly Agree (1). To be consistent with other items, they have to be reversed  $(1 \rightarrow 5, 2 \rightarrow 4, 3 \rightarrow 3, 4 \rightarrow 2, \text{ and } 5 \rightarrow 1)$  prior to calculating subscales and domains.

Domain	Subscale	Sum of Items	
Adolescent	Moodiness/Emotional Lability (MEL)	10 items (1, 6, 11, 16, 21, 26, 31, 36, 41, 46)	
Domain (AD)	Social Isolation/ Withdrawal (ISO)	10 items (2, 7, 12, 17, 22, 27, 32, 37, 42, 47)	
	Delinquency/Antisocial (DEL)	10 items (3, 8, 13, 18, 23, 28, 33, 38, 43, 48)	
	Failure to Achieve or Persevere (ACH)	10 items (4, 9, 14, 19, 24, 29, 34, 39, 44, 49)	
Parent Domain (PD)	Life Restrictions (LFR)	10 items (51, 52, 55, 56, 59, 63, 67, 71, 75, 79)	
	Relationship with Spouse/Partner (REL)	9 items (60, 64, 68, 72, 73, 76, 77, 80, 81)	
	Social Alienation (SOC)	7 items (53, 54, 57, 58, 61, 65, 69);	
	Incompetence/Guilt (INC)	8 items (62, 66, 70, 74, 78, 82, 86, 90)	
Adolescent- Parent Relationship Domain (APRD)		16 items (5, 10, 15, 20, 25, 30, 35, 40, 45, 50, 83, 84, 85, 87, 88, and 89)	

AD = MEL + ISO + DEL + ACH

PD = LFR + REL + SOC + INC

Total Parenting Stress (TS) = AD + PD + APRD

The last 22 items (91-112) with responses of 1=Yes and 0=No.

Life Stressors (LS) = Sum of last 22 items (Items 91-112)

TS, each domain, each subscale, and LS scale will be summarized by treatment group at visit 3 and 7 using descriptive statistics for continuous variable as described in Section 5.1.

Individual subject listings supporting the additional secondary endpoint summaries will be presented.

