6.2.3.4 Child Health Questionnaire Parent Form 28-Item (CHQ-PF28)

The Child Health Questionnaire Parent Form 28-item (CHQ-PF28) is a short generic measure of health status and health related quality of life (Landgraf 1996). CHQ-PF28 items have four, five, or six response options, divided over eight multi-item scales (physical functioning, general behavior, mental health, self-esteem, general health perceptions, parental impact: emotional, parental impact: time, and family activities) and five single item concepts (role functioning: emotional/behavior, role functioning: physical, bodily pain, family cohesion, and change in health). The CHQ-PF28 should be performed by the primary caregiver.

The CHQ-PF28 will be administered at Visit 3 and Visit 7.

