7,1.	Durante las últimas 4 semanas, ¿qué tan satisfecho(a) le parece que se ha sentido su hijo(a) con:	Muy satisfecho(a)	Algo satisfecho(a)	Ni satisfecho(a) ni insatisfecho(a)	Algo insatisfecho(a	ı) insati	Muy isfecho(a)
	a. Su capacidad escolar?						
	b. Sus amistades?						
SEC Las 8.1	 c. Su vida en general? CIÓN 8: LA SALUD DE SU HIJO(A) siguientes afirmaciones se refleren a la salue ¿Qué tan cierta o falsa es cada afirmació caso de su hijo(a)? 	er general.		ioluta- ente erta Bastante cierta	DIT C	Bastante	Absoluta- mente falsa
	 Parece que mi hijo(a) es menos sano(a niños que conozco.) que otros					
	b. Mi hijo(a) no ha estado nunca graveme	nte enfermo(a).					
360	 Me preocupo por la salud de mi hijo(a) otras personas se preocupan por la salu 	más de lo que ud de sus hijos((as).				

8.2 Comparando la salud presente de su hijo(a) con la de hace un año, ¿cómo la calificaría en general ahora?

	Mucho mejor ahora que hace un año	Algo mejor ahora que hace un año	Más o menos igual ahora que hace un año	Algo peor ahora que hace un año	Mucho peor ahora que hace un año
healthact chq	[name] Child Health Question	t reet, 16th Floor /	Boston, MA 0219 (CHQ-PF28) © 2007 Hea	9 / www.healthact	c hq.com Spanish (U.S.) Version – All rights reserved

4

9.1 Durante las últimas 4 semanas, ¿CUÁNTO sufrimiento emocional o preocupación le ha causado a USTED lo siguiente? Nada en absoluto Un poco Aigo Bastante Muco a. La salud física de su hijo(a) Image:		CION S. USTED I SUTAMILIA					

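### SAP 6.3, programmed as written, mis-scales the CHQ-PF28 z-scores, gives oppositely worded items one recode, and asks for a summary at a visit where the form is not given

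*SAP*

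**What the plan says.** SAP 6.3 scores the CHQ-PF28 in stages. Each item is recoded and rescaled: "The recorded score needs to be transformed in 0-100 range before calculating subscales and summary scores". A second table lists the items of each subscale under the heading *Sum of items* and gives a z formula for ten subscales, for example "PF_Z=(PF - 90.8525408) / 16.3826344" for Physical Functioning. The z-scores are then weighted into physical (PHS) and psychosocial (PSS) summary scores, which are put on a scale of 50 plus 10 times the raw value. For SNAP-IV the same section states a different rule explicitly: "Each subscale score is calculated by averaging the items scores within each subscale".

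In the item recode table, the row ending "8.1a-8.1c; 9.3a-9.3b" keeps the recorded code unchanged (1 to 1 through 5 to 5) for all three 8.1 items. The Spanish form in protocol Appendix 12.9 shows how they are worded. Item 8.1a begins "Parece que mi hijo(a) es menos sano(a" (the child seems less healthy than others). Item 8.1b begins "Mi hijo(a) no ha estado nunca" (the child has never been seriously ill). Item 8.1c says the parent worries more than other parents do.

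On timing, SAP 6.3 has the "z-score will be derived and be summarized by treatment group at visit 1 and 7", while protocol 6.2.3.4 says "The CHQ-PF28 will be administered at Visit 3 and Visit 7".

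**The concern.** A programmer who follows SAP 6.3 to the letter would produce wrong output in three ways.

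- **Scale.** A sum of two, three or four 0-100 items runs to 200, 300 or 400, but the norms subtracted from it are on a 0-100 scale. The z-score is the quantity to be reported, so losing its norm anchor damages the result itself. In PHS and PSS, the multi-item subscales would also carry 2 to 4 times their intended weight relative to the single-item ones (RP, BP, REB).
- **Direction.** One recode cannot serve items worded in opposite directions. Either 8.1b or the pair 8.1a and 8.1c enters General Health (GH) backwards.
- **Timing.** A Visit 1 summary would have no data, and the pre-dose Visit 3 scores would be left out. Protocol 9.2.2 defines the endpoint as the change from Visit 3 to Visit 7.

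**Working it through.** **Item range.** The item formulas are ((Final - 1)/4) x 100, ((Final - 1)/3) x 100 and ((Final - 1)/5) x 100. With codes 1 to 5, 1 to 4 and 1 to 6 respectively, each gives 0 at the minimum and 100 at the maximum. The SAP's stated 0-100 range therefore reproduces at item level.

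**Sum against mean.** Inputs are the norm mean, the SD and the item list for each subscale in the SAP 6.3 z table, with k the number of items.

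- Best possible health, sum: z = (100k - norm)/SD
- Best possible health, mean: z = (100 - norm)/SD
- Every item at the norm, sum: z = (k - 1) x norm/SD (should be 0)

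| Subscale | k | Norm mean | SD | Best health, sum | Best health, mean | At the norm, sum |
|---|---|---|---|---|---|---|
| PF | 3 | 90.8525 | 16.3826 | 12.77 | 0.56 | 11.09 |
| GH | 4 | 66.6958 | 19.3564 | 17.22 | 1.72 | 10.34 |
| PT | 2 | 83.8816 | 20.2902 | 5.72 | 0.79 | 4.13 |
| PE | 2 | 73.9788 | 21.4060 | 5.89 | 1.22 | 3.46 |
| SE | 3 | 79.2555 | 17.8308 | 12.38 | 1.16 | 8.89 |
| MH | 3 | 77.2596 | 13.6862 | 16.27 | 1.66 | 11.29 |
| BE | 4 | 72.3086 | 17.1448 | 19.11 | 1.62 | 12.65 |

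Example: BE at the norm is 3 x 72.3086/17.1448 = 12.65. RP, BP and REB have one item each, so sum and mean agree.

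Summing the untransformed items does not rescue the formulas. PF would run from (3 - 90.8525)/16.3826 = -5.36 to (12 - 90.8525)/16.3826 = -4.81, so every child would fall about five SDs below the norm.

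A 10-point arm difference in mean BE is 10/17.1448 = 0.58 z. Under the sum it prints as 40/17.1448 = 2.33 z. The between-child SD grows by the same factor of 4, so the standardized arm difference within the subscale does not change.

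Only the BE weight (.27911) is legible in the summary-score step. Taking it as a PSS weight, BE alone would add 0.27911 x 12.65 x 10 = 35.3 points to PSS for a child at the norm.

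**Item 8.1b.** CRF codes are not shown. The Spanish form prints 8.1 from true on the left to false on the right, so I take code 1 as definitely true. Other rows of the recode table fit left-to-right coding: 9.1 (from none at all), 8.2 (from much better) and 7.1 (from very satisfied) are reversed, while 6.1 (from all of the time) is not. With response r:

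- literal score = 25(r - 1); reversed score = 100 - 25(r - 1)
- error in GH (mean of 4 items) = (literal - reversed)/4

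| Response r | 1 | 2 | 3 | 4 | 5 |
|---|---|---|---|---|---|
| GH error, points | -25 | -12.5 | 0 | +12.5 | +25 |
| GH error, norm SDs (divided by 19.3564) | -1.29 | -0.65 | 0 | +0.65 | +1.29 |

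The healthiest child gets (100 + 0 + 100 + 100)/4 = 75, z = (75 - 66.6958)/19.3564 = 0.43, instead of 100, z = 1.72. The least healthy gets 25 (z -2.15) instead of 0 (z -3.45). The GH scale is compressed at both ends. If code 1 meant definitely false, 8.1a and 8.1c would be the reversed items instead.

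**Visits.** Protocol 6.2.3.4, protocol 9.2.2 and SAP Table 1 all place the form at Visits 3 and 7. SIPA shares its row in Table 1, and SAP 6.3 summarizes it at Visits 3 and 7. No CHQ-PF28 record is scheduled at Visit 1, so n = 0 in both arms. The screening fallback for baseline in SAP 5.1 does not help, because the form is not given at screening.

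**The case against.** The strongest case on the other side is that little depends on this. SAP 5.1 limits the analysis of the halted study to primary, key secondary and safety data, and the CHQ-PF28 is fifth of six additional secondary endpoints, with no test planned. *Sum of items* also heads rows with a single item, so it may merely list which items belong where. The SAP refers to the scoring manual for more detail, and z-scores of 12 to 19 would be noticed at once. The CRF codes are not in the documents, and the English 8.1 items are missing from the extracted form. The Visit 1 entry looks like a slip, and Visit 3 values would still be listed.

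Much of this limits the consequence, and it stands to that extent. It does not make the text right. SAP 5.1 leaves these endpoints out, yet 6.3 still specifies their summaries and supporting listings. In the SIPA table of the same section, the same heading does mean a sum, and for SNAP-IV averaging is stated. The manual is cited for further detail, not as overriding the rules given. For 8.1, no code direction suits all three items unless the CRF already stores 8.1b reversed, which nothing shows.

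**Conclusion.** The concern holds on all three points. The scaling error affects seven of the ten standardized subscales and both summary scores; direction and the standardized arm difference within a subscale survive. The effect on PHS and PSS as a whole cannot be sized from the legible weights.

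The 8.1b error reaches 25 GH points (1.29 norm SD) in level. This assumes code 1 is definitely true, no prior reversal on the CRF, and mean scoring. Its effect on change from Visit 3 to Visit 7 is probably small, because the item asks about history. The visit error needs no assumption; it corrupts no score but removes the baseline summary.

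Primary, key secondary and safety results are unaffected. The text should still be corrected before the scoring is programmed.

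**What to change.** 1. State in SAP 5.1 whether the SAP 6.3 summaries will be produced, so that the two sections agree.
2. If they will, replace the heading *Sum of items* in the CHQ-PF28 table by: mean of the transformed (0-100) items.
3. Check the CRF coding and the cited scoring manual, then move 8.1b to the reversed recode row (1 to 5 through 5 to 1).
4. Replace Visits 1 and 7 by Visits 3 and 7, and add change from Visit 3.

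A separate correction in the same section: the SIPA response key runs from strongly disagree = 5 to strongly agree = 1, and then from strongly disagree = 1 to strongly agree = 5. Keep only the key that matches the eCRF.

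The cost is a few lines of SAP wording and scoring code, with no new data.
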